4.7. DATA ANALYTIC PLAN

The primary purposes of a pilot study are to demonstrate safety, acceptability, and feasibility of methods and to determine important parameters with sufficient accuracy to allow reliable estimates of sample size, power, and detectable effects for a subsequent large-scale trial. Parameters include proportions for dichotomous endpoints (i.e. achieved 95% adherence over one-month); means and standard deviations for continuous endpoints (i.e. percentage of adherence over one month); and the spectrum of response profiles for longitudinal studies (i.e. adherence improvement or degradation). Thus, this pilot study aims to ensure that the parameters

for the larger trial are estimated as informatively as possible. We will estimate key study effect parameters with sample means and proportions together with 95% confidence intervals and test the primary null hypothesis at the two-sided level =.05.

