## 1. INTRODUCTION

The SMART Couple II study was designed to adapt a couples-based antiretroviral therapy (ART) adherence intervention for HIV-positive people who inject drugs (PWID) in Kazakhstan and their treatment support partners. The adapted intervention was then pilot tested among 66 HIV-positive PWID and their treatment support partners (n=66) to assess the feasibility and acceptability of the intervention and obtain preliminary estimates of adherence outcomes in the intervention arm versus the standard of care arm.

This document outlines the statistical analysis plan that will be followed to assess the adherence outcomes.

**Primary Outcome:** To evaluate the difference in ART adherence as measured through an electronic monitoring device (EMD) throughout the six-month follow-up between the intervention and standard of care arms.

**Secondary Outcome 1:** To evaluate the difference in biological measures of ART adherence (e.g., viral load, hair samples, dried blood spot testing) between the intervention and standard of care arms.

**Secondary Outcome 2:** To evaluate the difference in self-reported ART adherence as measured through a validated three-item adherence scale at the six-month follow-up between the intervention and standard of care arms.

**Secondary Outcome 3:** To evaluate the difference in uptake of opioid substitution therapy (OST) at the six-month follow-up between the intervention and standard of care arms.

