#### 4.5. Statistical Analysis Methods

Descriptive statistics of key independent variables and covariates will be summarized within each arm using frequencies or means (standard deviations) as appropriate. Overall participation rates will be reported in each arm based on the proportion of baseline participants who completed the six-month follow-up assessment.

To test **hypothesis 1 (H1)**, we will conduct t-tests to assess for differences in ART adherence rates over six months (0 to 180 days) between study arms.

To test **hypothesis 2 (H2)**, we will conduct chi-square tests to assess for differences in biological measures of ART adherence between study arms. Adjustments for small sample sizes will be made as appropriate.

To test **hypothesis 3 (H3)**, we will conduct generalized linear mixed modeling to assess for change in self-reported ART adherence from baseline to the six-month follow-up period and compare between arms. Generalized linear mixed modeling will be used to account for the effect of response clustering within participants. Models will adjust for the covariates specified above (section 4.4) and include random effects for dyad and intercept.

The model testing H3 is summarized as Equation H3:

$$\begin{aligned} \text{ART adherence} = & \text{Intercept} + B_1(\text{Arm}) + B_2(\text{Categorical variable corresponding to timepoint of adherence assessment; two degrees of freedom}) + \\ & B_3(\text{Arm * Timepoint of adherence assessment; two degrees of freedom}) + B_4(\text{Baseline adherence level}) + B_5(\text{Partner HIV status}) + B_6(\text{Respondent Age}) + B_7(\text{Respondent Sex}) + \text{Error} \\ & + \text{Random effects for the clustering within participant across timepoints and by dyad.} \end{aligned}$$

If the statistical test for the interaction between arm and timepoint is significant at the  $\alpha=0.05$  level, then we conclude that study arm significantly impacts the change in ART adherence. Within arm, adjusted estimates of changes in adherence will be presented along with 95% confidence intervals.

To test **hypothesis 4 (H4)**, we will conduct chi-square tests to assess for differences in uptake of OST between study arms. Adjustments for small sample sizes will be made as appropriate.

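### SAP 4.5 commits to no between-arm estimate with a confidence interval for any outcome, and for self-reported adherence it promises only within-arm changes

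*SAP*

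**What the plan says.** The SAP introduction gives as one aim to "obtain preliminary estimates of adherence outcomes in the intervention arm versus the standard of care arm". Protocol 4.7 describes a pilot as serving, besides safety, acceptability and feasibility, "to determine important parameters with sufficient accuracy to allow reliable estimates of sample size, power, and detectable effects for a subsequent large-scale trial". It then commits: "We will estimate key study effect parameters with sample means and proportions together with 95% confidence intervals", alongside a two-sided test of the primary null hypothesis.

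SAP 4.5 sets out the analyses:

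- H1, EMD adherence: "we will conduct t-tests to assess for differences in ART adherence rates over six months (0 to 180 days) between study arms".
- H2, biological measures: "we will conduct chi-square tests to assess for differences in biological measures of ART adherence between study arms".
- H3, self-reported adherence: a mixed model with an arm-by-time term. The decision rule begins "If the statistical test for the interaction between arm and timepoint is significant at the" 0.05 level, and the reporting rule is "Within arm, adjusted estimates of changes in adherence will be presented along with 95% confidence intervals".
- H4, OST uptake: "we will conduct chi-square tests to assess for differences in uptake of OST between study arms".

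SAP 4.1 names confidence intervals in its heading, but it has rules for descriptive summaries, p-values and rounding and none for intervals.

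**The concern.** A test result alone does not tell the next trial's designers how large the difference between arms was or how precisely it was measured. The SAP names a mean difference, risk difference, ratio or adjusted between-arm contrast with an interval for none of its four outcomes.

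For H3 the SAP does state what will be presented, and the quantity chosen cannot isolate the intervention. Index cases must be virally unsuppressed at entry (Protocol 4.4). Both arms receive the monitoring device, whose feedback the protocol itself says could help adherence (Protocol 4.6.6). Adherence could therefore rise in both arms for reasons unrelated to the sessions, and a within-arm change mixes those reasons with any effect of the intervention.

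The H3 decision rule may not fill the gap. Depending on how Equation H3 is read, its interaction test can miss a benefit that appears early and lasts, which would be a good result for this intervention.

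**Working it through.** **1. The plan's own figure.** The documents state no precision target. The nearest figure is 80% power with 30 dyads per arm at f = 0.15 (Protocol 4.6.12). Take the within-between interaction with N = 60, two arms and four assessments, and assume a within-person correlation of 0.5 and sphericity (neither is stated). The noncentrality is f² × N × m/(1 − ρ) = 0.0225 × 60 × 4/0.5 = 10.8, on 3 and 174 degrees of freedom, and power is 0.786. The stated figure reproduces to within two points. It concerns a test, so it neither supplies nor replaces an effect estimate.

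**2. What Equation H3 tests.** SAP 4.3 lists four assessment times. If all four were outcomes, time would need three degrees of freedom. The equation gives two and enters baseline adherence as a covariate. The literal reading is that the outcomes are the three follow-ups: IPI, 3 months and 6 months. With IPI as the reference level, the adjusted difference between arms is:

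- at IPI: B1
- at 3 months: B1 + B3(3m)
- at 6 months: B1 + B3(6m)

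Suppose the benefit is δ at every follow-up. Then B1 = δ and both B3 terms are 0. The interaction null is true whatever the size of δ, so the decision rule has no power against a constant benefit beyond its 5% error rate. The coefficient that carries the benefit, B1, has no stated test or interval.

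If baseline was meant to be an outcome time, the interaction would capture differences in change. Time would then need three degrees of freedom, and baseline would sit on both sides of the equation. The SAP does not settle which was intended.

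**3. Width of the unreported intervals.** Inputs: 30 analysed per arm (Protocol 4.6.12), taking one analysed participant per dyad (assumption).

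Mean difference, unadjusted: half-width = t(0.975, 2n − 2) × SD × √(2/n). At n = 30 this is 2.002 × 0.258 = 0.52 SD. It is 0.49 SD at 33 per arm and 0.55 SD at 27 (30 less a further 10%, as sensitivity). The documents give no SD for EMD days on the 0 to 180 scale, so a range is shown:

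- SD 20 days: 0.517 × 20 = about 10 days
- SD 40 days: 0.517 × 40 = about 21 days
- SD 60 days: 0.517 × 60 = about 31 days

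Difference in proportions: half-width = 1.96 × √(p1q1/n + p2q2/n), used here only to show size. With n = 30 and assumed rates:

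- 10% v 20%: 1.96 × √(0.09/30 + 0.16/30) = about 18 points
- 50% v 50%: 1.96 × √(0.25/30 + 0.25/30) = about 25 points

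For comparison, an unadjusted single-arm mean has half-width t(0.975, 29) × SD/√30 = 0.37 SD. The between-arm interval is about 0.52/0.37 = 1.4 times as wide, so within-arm intervals understate the uncertainty in the comparison that matters.

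**The case against.** The strongest reply is that little is lost. Protocol 4.7 already promises effect parameters with intervals, and nothing in the SAP withdraws it. The H1 t-test is built on the mean difference, and the H3 model contains the arm contrasts. SAP 4.1 plans means with SDs and counts with percentages. If outcomes are summarised that way by arm, a reader could work out the H1 difference and the H2 and H4 risk differences. A pilot also has other purposes, with safety, feasibility and acceptability among its primary ones.

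Much of this stands, and it rules out three stronger readings that a reader might infer:

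- That the pilot will not produce an intervention-versus-SOC estimate. The planned analyses contain or directly yield the contrasts. What is missing is a commitment to report them.
- That the SAP will judge the intervention by comparing two before-after intervals side by side. The within-arm sentence concerns H3 only, and the stated conclusion for H3 rests on the interaction test, which compares arms.
- That the tests will mostly fail to reject. The documents give no SDs or outcome rates from which to show this.

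The reply does not close the gap. Sample means and proportions in Protocol 4.7 can be read as arm-level values, and the SAP should resolve that. SAP 4.5 lists by-arm summaries for independent variables and covariates, not for outcomes. A chi-square test yields no effect estimate, and no effect measure is chosen for H2 or H4. The adjusted H3 contrasts cannot be recovered from summary tables.

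**Conclusion.** The point holds as a reporting omission with one substantive consequence. SAP 4.5 does not carry the protocol's commitment through to a between-arm estimate with an interval for any outcome, and its one reporting rule on intervals, for H3, names a different quantity. On the literal reading of Equation H3, a constant benefit would have neither a test nor an interval. That conclusion depends on the two degrees of freedom for time and the baseline covariate being meant as written.

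The unreported intervals would be wide: about ±0.52 SD for an unadjusted mean difference at 30 per arm, and roughly ±18 to ±25 percentage points for proportions at the assumed rates. The SDs and rates are assumptions. The figures do not apply directly to the adjusted H3 model, whose precision depends on correlations the documents do not give. The change is worth making before results are reported; the design and data collection are unaffected.

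**What to change.** Amend SAP 4.5 so that each analysis names its estimate, always intervention minus SOC:

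- **H1:** mean difference in EMD days with 95% CI, and the SD in each arm.
- **H2 and H4:** risk difference with a 95% CI suited to small samples. A Newcombe score interval is one option.
- **H3:** replace the within-arm sentence with the adjusted between-arm difference at IPI, 3 and 6 months, each with a 95% CI. These are B1 and its sums with the matching B3 terms. The six-month contrast should be identified as the one that answers the hypothesis. Within-arm changes may stay, labelled as descriptive.

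State in Equation H3 which assessments are outcomes, so that the degrees of freedom for time and the role of baseline agree. Add one line to SAP 4.1 saying that 95% intervals accompany all between-arm comparisons. Reporting the H3 variance components would help plan the next trial but is optional. The dyad component may be poorly estimated, because partners may be HIV-negative and only dyads with two HIV-positive members would inform it.

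The cost is SAP wording and a few extra lines of output. No new data are needed, and the estimates come from the planned models or the same two-by-two tables.

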#### 4.6. Missing Data

The analysis sample is restricted to participants with data for the outcomes and with complete demographic information. Missing data for outcomes or demographics will not be imputed.

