4.6.11. Safety, Acceptability, Feasibility, Retention and Implementation Data. Intervention safety will be assessed through adverse event reporting by study and clinic staff and an exit interview asking about any negative experiences during the intervention. We will assess acceptability and feasibility of the adapted intervention and biological testing. Both partners will be assessed at the end of each intervention session on satisfaction and obstacles to participation. A brief survey will ask about participants' experiences with biological sample collection. We will track the number of participants retained in the study. For those who drop out, we will attempt to contact them to determine the reason. Staff will be asked questions about intervention delivery, specimen collection and challenges and facilitators of implementation.

4.6.12. Sample size and power considerations for the pilot RCT. We can estimate power for this study based on previous studies.^{33,35} Based on Project Renaissance attrition rates,³³ we anticipate there will be no more than 10% attrition throughout the study. Power analyses were conducted with G*Power⁴⁹ (v3.1.0) using a repeated measures within-between ANOVA approach and $\alpha=.05$. With 30 dyads per arm, we would have 80% power to detect a medium effect size ($f=.15$). Thus, we will recruit 66 couples and aim to have 60 for analysis.

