### **3.2.3. Biological Measures.**

*Dried blood spot (DBS) samples* were collected from HIV-positive participants at their regular AIDS Center visit to assess feasibility and acceptability of the biological collection process and measure biological levels of medication. A nurse collected DBS samples by venipuncture, using a pipette to spot blood directly onto Whatman 903 ProteinSaver cards. The cards will be air-dried, individually packaged in a plastic bag with desiccant, and transferred to a -20 to -80°C freezer for storage. Only samples of participants on tenofovir-based regimens were shipped to the US.

*Hair samples.* Participants self-collected hair samples at baseline and immediately post-intervention to measure ART adherence levels. To collect hair samples, participants cut a small thatch of hair (~50 strands of hair) close to the scalp from a bottom layer of their hair. Hair was placed in a piece of tinfoil and inside a Ziploc bag labeled with their study ID. Participants shipped samples to GHRCCA staff, who then batch shipped samples to the US for testing.

*Viral load.* Participants are tested for viral load levels during every patient visit at the AIDS Center, which occurs every six months. Viral load data were abstracted from the AIDS Center electronic medical record at the closest visit prior to the baseline assessment and at the closest visit to the six-month follow-up assessment.

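### SAP 4.6 sets one analysis sample for every hypothesis, so a missing demographic item excludes randomised participants from unadjusted tests that use no demographics, and its outcome condition can be read in two ways

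*SAP*

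**What the plan says.** SAP 4.6 has two sentences. The first sets the sample: "The analysis sample is restricted to participants with data for the outcomes and with complete demographic information". The second says "Missing data for outcomes or demographics will not be imputed". No separate sample is given for each hypothesis, and the SAP does not list which demographic items must be present.

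SAP 4.5 gives the tests:

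- H1 (primary, electronic monitoring device): "we will conduct t-tests to assess for differences in ART adherence rates over six months (0 to 180 days) between study arms".
- H2 (biological measures): "we will conduct chi-square tests to assess for differences in biological measures of ART adherence between study arms".
- H3 (self-reported adherence): a mixed model over visits. "Models will adjust for the covariates specified above (section 4.4) and include random effects for dyad and intercept". The covariates in 4.4 are age, sex, partner HIV status and baseline adherence.
- H4 (opioid substitution therapy): "we will conduct chi-square tests to assess for differences in uptake of OST between study arms".

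On the biological measures, SAP 3.2.3 says of the dried blood spots: "Only samples of participants on tenofovir-based regimens were shipped to the US". On loss to follow-up, Protocol 4.6.12 says "we anticipate there will be no more than 10% attrition throughout the study" and plans 66 dyads so that 60 can be analysed.

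Neither document names an intention-to-treat set, a missing-data assumption, a rule for partial device follow-up, or a missing-data sensitivity analysis.

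**The concern.** A comparison of randomised arms should keep everyone whose data the test can use. Dropping a participant from a t-test of device-opening days because a demographic item is blank removes information and moves the analysed set away from the randomised set, with nothing in return.

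The outcome condition is a second problem because it does not say which outcomes. If it means the outcome under test, little changes. If it means all of them, exclusions would depend on drug regimen and on which samples arrived. Leaving this open allows the sample to be settled after the data are seen.

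The outcome is adherence, so people who stop supplying data may well be the less adherent. If such loss differs by arm, a complete-case comparison can be biased. Protocol 4.7 also says that the pilot is meant to supply parameters for a larger trial, which is a further reason not to discard usable data.

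**Working it through.** **1. Which tests need demographics (SAP 4.5 against 4.6)**

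| Hypothesis | Test | Uses a demographic variable? | Subject to the 4.6 condition? |
|---|---|---|---|
| H1 | t-test | No | Yes |
| H2 | chi-square | No | Yes |
| H3 | mixed model | Yes: age, sex, partner HIV status | Yes |
| H4 | chi-square | No | Yes |

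SAP 4.4 adjusts only where appropriate, but that governs covariates, not who is analysed. The mismatch for H1, H2 and H4 follows from the wording alone.

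**2. The plan's own power figure.** Protocol 4.6.12 states 80% power with 30 dyads per arm, f = 0.15, two arms and a repeated-measures within-between ANOVA. The correlation between visits is not stated. I assume ρ = 0.5, sphericity and m = 4 assessments.

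- λ = f²·N·m/(1−ρ) = 0.0225 × 60 × 4 / 0.5 = 10.8
- df = (2−1)(4−1) = 3 and (60−2)(4−1) = 174
- Power = 78.6%, close to the stated 80%. It ranges from 62.6% at ρ = 0.3 to 95.5% at ρ = 0.7.

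**3. Room for further loss.** 66 × 0.90 = 59.4, so the allowance covers the anticipated attrition and nothing else. Let q be an extra proportion lost to the sample rule. The documents give no value, so the q values are assumptions. Kept = 66 × 0.90 × (1−q). The t-test column is the difference detectable with 80% power, two-sided 0.05, from the noncentral t with df = 2n−2 and noncentrality d/√(2/n).

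| q | Kept of 66 | Nearest n per arm | H1 detectable difference | Power at f = 0.15 (ρ = 0.5) |
|---|---|---|---|---|
| 0 | 59.4 | 30 | 0.74 SD | 78.6% |
| 5% | 56.4 | 28 | 0.76 SD | 75.4% |
| 10% | 53.5 | 27 | 0.78 SD | 73.6% |
| 20% | 47.5 | 24 | 0.83 SD | 67.8% |

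Confidence intervals widen by √(30/n): about 5% at 27 per arm and 12% at 24. If demographics are nearly complete, the demographic condition alone would put q near zero.

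**4. Bias if H3 were restricted to complete cases.** This is a simulation under assumptions: 33 per arm, four visits, ρ = 0.5, 5% missing demographics at random, and log-odds of dropout after the second visit rising 1.5 per SD of lower score at the preceding visit (2,500 replicates). It is a simplified stand-in for H3, with baseline as a response and no dyad effect. The same model was fitted to complete cases and to all available visits. The estimate is the arm difference at the last visit, in SD.

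| True effect | Dropout | Retained, SOC / intervention | Complete cases | All visits |
|---|---|---|---|---|
| 0 | about 10%, equal | 89% / 89% | 0.002 | 0.002 |
| 0 | about 10%, differential | 82% / 93% | −0.034 | 0.001 |
| 0 | about 20%, differential | 71% / 85% | −0.042 | 0.000 |
| 0.50 | about 10% | 89% / 94% | 0.485 | 0.500 |
| 0.50 | about 10%, differential | 82% / 96% | 0.454 | 0.497 |
| 0.50 | about 20%, differential | 70% / 91% | 0.446 | 0.507 |

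The shift is about zero with equal dropout and no effect, and at most about 0.06 SD here. Its sign would reverse if the intervention arm lost more people. The all-visits result relies on dropout depending only on observed scores.

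**The case against.** The case for leaving the text alone has real strength.

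- **Demographic loss is likely to be small.** Age is an eligibility item (Protocol 4.4), the index participant's sex is used to balance randomisation (4.6.1), baseline is completed before randomisation, and each question must be answered or refused (5.1). This stands. Refusal is allowed (6.4.1), so the loss need not be zero.
- **Completeness is asked only of demographics.** For outcomes, 4.6 asks for data, not for every outcome or visit. Declining to impute is compatible with a likelihood mixed model on all available visits. This stands. A reader might infer that the SAP discards partial follow-up, but it states no such rule.
- **An all-outcomes rule would defeat the plan's own target.** A reader might multiply availability rates. Assuming 50–90% on tenofovir, 60–95% returning hair and 80–95% with a viral load, retention is 0.50 × 0.60 × 0.80 = 24% to 0.90 × 0.95 × 0.95 = 81%. The rates are assumed, and the reading conflicts with the aim of analysing 60 of 66 dyads. It is possible but not the natural one.
- **A large bias in the primary outcome is not shown.** With no true effect, an assumed SD of 45 days and dropout of 4–7% against 17–24%, a completers-only comparison can show a spurious 3.1 to 7.5 days, or 0.07 to 0.17 SD. That dropout averages above the anticipated 10%. The device also records passively, so leaving the surveys is not the same as missing device data. An available-case main analysis would not remove this bias either.
- **Some of the remedy is already planned.** Six-month completion by arm will be reported (SAP 4.5), and retention and reasons for dropout tracked (Protocol 4.6.11). This stands, but neither defines the analysis set.

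**Conclusion.** The point holds in a limited form. As written, 4.6 applies a demographic condition to three unadjusted tests, including the primary one, that do not use demographics. That rests on the wording alone. The resulting loss is unknown and probably small.

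The wording on outcomes is ambiguous. Loss of participants without a dried blood spot assay from the primary analysis, and loss of partial follow-up from H3, arise only on the all-outcomes reading, which the text permits but does not compel. Bias is a risk, not a finding: it needs dropout that is related to adherence and differs by arm, and the documents give no rates from which to size it. This is a cheap improvement that should be made before analysis. It does not show that the planned results would be invalid.

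**What to change.** Replace the text of SAP 4.6 with:

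> Each outcome is analysed by assigned arm in all randomised participants eligible for that outcome who have data for it. Missing demographics do not exclude anyone from an unadjusted analysis. The H3 model is fitted by maximum likelihood to all available visits.

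Then:

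- Add a sensitivity analysis for missing outcomes, at least for the primary device outcome, for example multiple imputation with a downward shift for those who drop out. It is needed because the available-case main analysis does not itself remove bias from informative dropout.
- State what counts as having device data, and how days after loss of signal or withdrawal are treated.
- Report missingness by arm for each outcome.

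Whether HIV-positive partners belong in these analyses is a separate question that this wording leaves open. The cost is a few sentences in the SAP and a little extra analysis, with no new data.
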